- e) **Thyroid Disorders:** Pembrolizumab can cause thyroid disorders, including hyperthyroidism, hypothyroidism and thyroiditis. Hyperthyroidism occurred in 96 (3.4%) of 2799 patients receiving pembrolizumab, including Grade 2 (0.8%) and Grade 3 (0.1%) hyperthyroidism. The median time to onset was 1.4 months (range: 1 day to 21.9 months), and the median duration was 2.1 months (range: 3 days to 15.0+ months). Hyperthyroidism led to discontinuation of pembrolizumab in 2 (<0.1%) patients. Hyperthyroidism resolved in 71 (74%) of the 96 patients. Hypothyroidism occurred in 237 (8.5%) of 2799 patients receiving pembrolizumab, including Grade 2 (6.2%) and Grade 3 (0.1%) hypothyroidism. The median time to onset was 3.5 months (range: 1 day to 18.9 months), and the median duration was not reached (range: 2 days to 27.7+ months). Hypothyroidism led to discontinuation of pembrolizumab in 1 (<0.1%) patient. Hypothyroidism resolved in 48 (20%) of the 237 patients. The incidence of new or worsening hypothyroidism was higher in patients with HNSCC occurring in 28 (15%) of 192 patients receiving pembrolizumab, including Grade 3 (0.5%) hypothyroidism. Of these 28 patients, 15 had no prior history of hypothyroidism. Thyroiditis occurred in 16 (0.6%) of 2799 patients receiving pembrolizumab, including Grade 2 (0.3%) thyroiditis. The median time of onset was 1.2 months (range: 0.5 to 3.5 months).
- f) **Type 1 Diabetes mellitus:** Pembrolizumab can cause type 1 diabetes mellitus, including diabetic ketoacidosis, which has been reported in 6 (0.2%) of 2799 patients receiving pembrolizumab. Monitor patients for hyperglycemia or other signs and symptoms of diabetes. Administer insulin for type 1 diabetes and withhold pembrolizumab and administer antihyperglycemics in patients with severe hyperglycemia.
- g) **Immune-Mediated Nephritis and Renal Dysfunction:** Pembrolizumab can cause immune-mediated nephritis. Monitor patients for changes in renal function. Nephritis occurred in 9 (0.3%) of 2799 patients receiving pembrolizumab, including Grade 2 (0.1%), Grade 3 (0.1%), and Grade 4 (<0.1%) nephritis. The median time to onset was 5.1 months (range: 12 days to 12.8 months), and the median duration was 3.3 months (range: 12 days to 8.9+ months). Eight (89%) of the 9 patients received systemic corticosteroids, with 7 of the 8 receiving high-dose corticosteroids for a median duration of 15 days (range: 3 days to 4.0 months) followed by a corticosteroid taper.

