- Interruption of cabozantinib treatment for AEs may occur at any time per investigator discretion. If treatment is interrupted due to AEs for more than 6 weeks, patient will be taken off study unless the investigator deems there to be previous or ongoing clinical benefit.
- Dose interruptions for reason(s) other than AEs (eg, surgical procedures) can be longer than 6 weeks but require Sponsor approval. The acceptable length of interruption will depend on agreement between investigator and the Sponsor.
- Dose interruptions may occur in 2 ways:
 - Within a cycle:** If dosing interruption and/or dose reduction occurs between Day 1 and Day 21 of a cycle (including protocol-specified windows), the cycle proceeds as planned.
 - Prior to the initiation of a new cycle:** If the investigator decides on day 1 of a new cycle that dose interruption should occur, that cycle may be delayed. When the investigator decides that dosing should resume, the day that the patient restarts drug will be day 1 of that new cycle. Re-escalation to any previous dose may be allowed at the discretion of the investigator no sooner than 2 weeks beyond resolution of AEs that led to the dose reduction. Dose re-escalation is not allowed for a previous dose reduction triggered by Grade 4 hematologic toxicities or by Grade 4 AEs affecting major organs (eg, central nervous system, cardiac, hepatic, renal).

Table 4: Dose Modifications of Cabozantinib for Treatment Related AEs

CTCAE v4.0	Recommended Guideline for Management
Grade 1 AEs	Supportive care as indicated. Continue cabozantinib at the current dose level if AE is manageable and tolerable.
Grade 2 AEs which are tolerable and are easily managed	Continue cabozantinib at the current dose level with supportive care.
Grade 2 AEs which are intolerable and cannot be adequately managed	At the discretion of the investigator, cabozantinib should be dose reduced or interrupted. Note: It is recommended that dose holds be as brief as possible.
Grade 3 AEs (except clinically non-relevant laboratory abnormalities)	Cabozantinib should be interrupted unless the toxicity can be easily managed with a dose reduction and optimal medical care. Note: It is recommended that dose holds be as brief as possible
Grade 4 AEs (except clinically non-relevant laboratory abnormalities)	Subjects should have cabozantinib interrupted immediately.

Discontinue cabozantinib unless the following criteria are met:

<

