6.2.1 CABOZANTINIB

The side effect profile of cabozantinib includes GI symptoms (such as nausea, vomiting, and diarrhea), fatigue/asthenia, anorexia, weight loss, skin rash including PPE syndrome, mucosal inflammation/stomatitis, and hypertension. Subjects may also experience medically important but less frequent adverse events including arterial and venous thrombotic events such as deep vein thrombosis (DVT), pulmonary embolism (PE), transient ischemic attack, and myocardial infarction; severe hemorrhagic events, proteinuria, wound healing complications, GI perforation, intraabdominal and pelvic abscess, GI and non-GI fistulae formation, osteonecrosis, and reversible posterior leukoencephalopathy syndrome (RPLS).

Common laboratory abnormalities reported as AEs include ALT increased, AST increased, TSH increased, hypokalemia, hypomagnesemia, hypophosphatemia, hypocalcemia, lipase increased, and thrombocytopenia.

Please refer to the Investigator's Brochure for additional details.

As with all investigational products, unknown AEs may occur. Subjects should be monitored closely for all AEs. The predicted effective plasma half-life of cabozantinib is 99 hours.

Thus, when initiating therapy with cabozantinib, it will take most subjects 2-3 weeks to reach steady state. If AEs attributable to cabozantinib occur within the initial 3-week period of dosing, early intervention with dose modifications may be justified for AEs that, if worsened, could potentially be dangerous or debilitating, since without a dose adjustment, systemic exposure of cabozantinib might be expected to increase after the onset of the AE.

Cabozantinib should be discontinued for the following adverse events: visceral perforation or fistula formation, severe hemorrhage, serious arterial thromboembolic events (e.g MI, cerebral infarction), nephrotic syndrome, malignant hypertension, hypertensive crisis, persistent uncontrolled hypertension despite optimal medical management, osteonecrosis of the jaw (ONJ), and RPLS.

Management of gastrointestinal disorders, hepatobiliary disorders, hematological disorders, fatigue, anorexia, weight loss, skin disorders, hypertension, thromboembolic events,

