Other endocrine disorders such as hypocalcemia, hyperglycemia, and hypoglycemia, and associated laboratory changes, have been observed in single agent cabozantinib studies. Monitoring with standard laboratory tests for endocrine disorders and clinical examination prior to initiation and during treatment with cabozantinib is recommended. Cabozantinib should be discontinued in subjects with severe or life-threatening endocrine dysfunction.

HEMORRHAGIC EVENTS

Hemorrhagic events including serious and sometimes fatal events have been reported with cabozantinib. In order to mitigate risk of severe hemorrhage, subjects should be evaluated for potential bleeding risk factors prior to initiating cabozantinib treatment and monitored for bleeding events with serial complete blood counts and physical examination while on study. Risk factors for hemorrhagic events may include (but may not be limited to) the following:

- Tumor in the lung with cavitary lesions or tumor lesions which invade or encase major blood vessels. NSCLC with squamous cell differentiation is known for significant lung cavitations and centrally located tumors that may invade major blood vessels. Thus, the anatomic location and characteristics of tumor as well as the medical history must be carefully reviewed in the selection of subjects for treatment with cabozantinib.
- Recent or concurrent radiation.
- Active peptic ulcer disease, inflammatory GI diseases including Crohn's disease and ulcerative colitis
- Underlying medical conditions which affect normal hemostasis (eg, deficiencies in clotting factors and/or platelet function, or thrombocytopenia)
- Concomitant medication with anticoagulants or other drugs which affect normal hemostasis
- History of clinically significant hemoptysis, hematemesis, or hematuria

Cabozantinib should be discontinued in subjects with serious and life-threatening bleeding events or persistent, clinically significant hemoptysis or hematemesis

GI PERFORATION/FISTULA AND NON-GI FISTULA FORMATION

GI perforation/fistula and non-GI fistula formation have been reported with cabozantinib. Carefully monitor for episodes of abdominal pain, nausea, emesis, constipation, and fever especially in subjects with known risk factors for developing GI perforation/fistula or non-GI fistula, to allow for early diagnosis. Such risk factors include (but may not be limited to) the following:

- Intra-abdominal tumor/metastases invading GI or respiratory tract

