8.3.3 CLASSIFICATION OF AN ADVERSE EVENT

8.3.3.1 SEVERITY OF EVENT

An investigator who is a qualified physician will evaluate all adverse events as to:

CTCAE V 4.0	
Grade 1	Mild; asymptomatic or mild symptoms; clinical or diagnostic observations only; intervention not indicated.
Grade 2	Moderate; minimal, local or noninvasive intervention indicated; limiting age-appropriate instrumental ADL.

Grade 3	Severe or medically significant but not immediately life-threatening; hospitalization or prolongation of hospitalization indicated; disabling; limiting self-care ADL.
Grade 4	Life threatening consequences: urgent intervention indicated.
Grade 5	Death related to AE

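### For Grade 3 bleeding and Grade 3 endocrine dysfunction, the stop rules in section 6.2.1 and Table 4 give different instructions for cabozantinib, and no text says which governs

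*Combined protocol and SAP*

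**What the plan says.** Three texts govern cabozantinib after a bleed.

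- The general stop list near the start of section 6.2.1: "Cabozantinib should be discontinued for the following adverse events: visceral perforation or fistula formation, severe hemorrhage". The list continues with other events. For hemorrhage it gives no exception and no route back to treatment.
- The Hemorrhagic Events text later in 6.2.1: "Cabozantinib should be discontinued in subjects with serious and life-threatening bleeding events or persistent, clinically significant hemoptysis or hematemesis".
- Table 4 in section 6.1.2.3, which covers all treatment-related adverse events by grade. At Grade 3: "Cabozantinib should be interrupted unless the toxicity can be easily managed with a dose reduction and optimal medical care". At Grade 4: "Subjects should have cabozantinib interrupted immediately", and then "Discontinue cabozantinib unless the following criteria are met". The two criteria are clear clinical benefit in the investigator's judgment, and toxicity manageable at a reduced dose after recovery to Grade 1 or baseline.

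Two texts govern endocrine events. The thyroid and endocrine text in 6.2.1 says "Cabozantinib should be discontinued in subjects with severe or life-threatening endocrine dysfunction". Table 4 applies as above, with no endocrine exception. The 6.2.1 stop list does not mention endocrine events.

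Section 8.3.3.1 describes Grade 3 as "Severe or medically significant but not immediately life-threatening" and Grade 4 as life-threatening. Section 6.2 opens by calling its contents general guidelines, to be applied as the treating provider thinks clinically indicated. Table 4's own column heading also calls it a recommended guideline.

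**The concern.** A treating physician with a patient who has had a related Grade 3 bleed, or related Grade 3 endocrine dysfunction, gets a different instruction depending on which page is read. One page ends cabozantinib; another permits a hold or a reduced dose and later re-exposure. Sections 2.3.1.1 and 6.2.1 both describe hemorrhage on cabozantinib as sometimes fatal, so whether re-exposure is allowed should not depend on which page is consulted.

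There is also a reporting consequence. Section 9.4.4 tabulates adverse events leading to premature discontinuation of the study intervention. If the same event can lead to a stop or to an interruption under the protocol, that table partly reflects which text was followed.

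**Working it through.** The protocol gives no figure to reproduce here. The main check sets the texts side by side by grade, using the scale in 8.3.3.1.

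| Treatment-related event | 6.2.1 stop list | 6.2.1 event-specific text | Table 4 |
|---|---|---|---|
| Grade 3 bleed, other than persistent hemoptysis or hematemesis | Discontinue | Depends on reading (below) | Interrupt or reduce |
| Grade 3 persistent, clinically significant hemoptysis or hematemesis | Discontinue (severe) | Discontinue | Interrupt or reduce |
| Grade 4 bleed | Discontinue | Discontinue | Interrupt at once; discontinue unless both criteria are met |
| Grade 3 endocrine dysfunction | Not listed | Discontinue | Interrupt or reduce |
| Grade 4 endocrine dysfunction | Not listed | Discontinue | Interrupt at once; discontinue unless both criteria are met |

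**The hemorrhage sentence.** Its first limb joins *serious* and *life-threatening*.
- Read jointly, a Grade 3 bleed does not reach the threshold, because Grade 3 is by definition not immediately life-threatening.
- Read as either one, a Grade 3 bleed that meets a seriousness criterion, such as hospitalization, is a stop.
- Section 8.3.2 makes every life-threatening event serious. On the joint reading *serious* therefore adds nothing, and on the either-one reading *life-threatening* adds nothing. The wording does not settle the matter.

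**Where the rows conflict.**
- Grade 3 bleeding: the stop list and Table 4 disagree whichever way the hemorrhage sentence is read. On the joint reading, that sentence also differs from the stop list in its own section.
- Grade 3 endocrine dysfunction: a two-way conflict, event text against Table 4.
- Grade 4, either type: the default is the same everywhere. The difference is confined to the exception, which only Table 4 offers.

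**Precedence.** No text says whether Table 4 or the event-specific text governs, or whether the Grade 4 exception reaches events on the stop list.

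**Size.** Inputs: Grade 3 or higher hemorrhage in 3% on cabozantinib (section 2.3.1.1) and 44 phase 2 patients (section 9.2).
- Expected bleeds of Grade 3 or higher: 44 × 0.03 = 1.32.
- Chance of at least one: 1 − 0.97^44 = 0.738, about 74%.

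Both are upper bounds for the Grade 3 conflict if the rate carries over, because the 3% includes Grade 4 and 5 events. Phase 1b patients are not counted. No comparable endocrine figure is offered: the type 1 diabetes rate in section 2.3.1.2 is not graded, so a total of severe endocrine events cannot be formed from it.

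**The case against.** The strongest defence has three parts.

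**These are guidelines.** The opening of 6.2 and the heading of Table 4 leave decisions to the treating provider, and section 7.2 lets the investigator withdraw treatment for any adverse event that warrants it. This stands as far as it goes: nobody is forced into an unsafe choice. But discretion to depart from a default is not a default. The opening statement also sits after Table 4 and does not rank the two.

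**Specific text overrides the general table.** Where 6.2.1 wants the general scheme to apply, it says so: the hepatobiliary text refers to Table 4 and the electrolyte text to 6.1.2.3. The bleeding and endocrine texts contain no such pointer. This is a reasonable inference, and it would resolve the endocrine row if it were written down. It does not resolve bleeding, because the two texts inside 6.2.1 are worded differently from each other. Nor can the stop list be assumed absolute: it lists osteonecrosis of the jaw for discontinuation, while the Osteonecrosis text in the same section interrupts for any documented case and allows re-initiation with approval.

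**Severe is not tied to a grade in 6.2.1.** This is true; the mapping to Grade 3 comes from 8.3.3.1. If the authors meant something else, the text needs to say what.

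Some stronger inferences fail.
- A reader might infer that the hemorrhage text stops only for life-threatening bleeding. It also stops for persistent, clinically significant hemoptysis or hematemesis.
- A reader might infer that Table 4 never goes beyond interruption. At Grade 4 it discontinues by default.
- A reader might treat severe diabetes as a contradiction, because section 2.3.1.2 says to "withhold pembrolizumab and administer antihyperglycemics in patients with severe hyperglycemia" while 6.2.1 stops cabozantinib. These are instructions for two different drugs and can both be followed. What remains is only that 6.2.1 does not say whether its endocrine rule is limited to cabozantinib-related events.
- A reader might infer that early stopping removes patients from response assessment. Section 7.2 keeps patients who leave treatment for reasons other than progression on the scan schedule until progression, unless they withdraw consent to follow-up.

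**Conclusion.** The inconsistency is real and limited. It is a conflict of instruction at Grade 3 for bleeding and for endocrine dysfunction, a further wording difference between the two bleeding thresholds in 6.2.1, and at Grade 4 a difference only in whether an exception exists. Opposite outcomes across all grades, or an identical conflict for the two event types, would be more than the texts support.

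At most about 1.3 of 44 phase 2 patients would be expected to have a bleed to which the conflict could apply. This assumes that the 3% in section 2.3.1.1 holds for this combination and population. The 74% is the chance of any bleed of Grade 3 or higher under that assumption, not the chance that the Grade 3 conflict arises.

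The conclusion also rests on reading *severe* as Grade 3, as 8.3.3.1 does. The consequences are for patient management and for the table of adverse events leading to discontinuation. The sample size, alpha, power and response follow-up are untouched. It should be corrected because it concerns re-exposure after a potentially dangerous event and costs little to settle.

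**What to change.** Reconcile section 6.1.2.3 (Table 4) with the stop list, the Hemorrhagic Events text and the endocrine text in 6.2.1:

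1. Give bleeding and endocrine dysfunction each one consistent instruction for cabozantinib by CTCAE grade, and reword the hemorrhage sentence so that it can be read only one way.
2. State whether the event-specific text or Table 4 governs when they differ.
3. State whether Table 4's Grade 4 exception applies to events on the 6.2.1 stop list.
4. State whether the endocrine rule is limited to cabozantinib-related events.
5. In the same pass, check the bleeding instruction under Thromboembolic Events, which interrupts cabozantinib for clinically relevant bleeding during anticoagulation, and the osteonecrosis wording against the stop list.

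The clinical team chooses the outcomes; this point does not say which instruction is right. The cost is an amendment to protocol wording, with no change to the sample size, assessments or analysis.

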6.3 PREPARATION/HANDLING/STORAGE/ACCOUNTABILITY

6.3.1 ACQUISITION AND ACCOUNTABILITY

Drug accountability and subject compliance will be assessed with drug dispensing and return records.

Study Drug Accountability: The investigator will maintain accurate records of receipt of all cabozantinib, including dates of receipt. In addition, accurate records will be kept regarding when and how much study treatment is dispensed and used by each subject in the study.

Reasons for deviation from the expected dispensing regimen must also be recorded. At completion of the study, to satisfy regulatory requirements regarding drug accountability, all unused cabozantinib will be reconciled and destroyed in accordance with applicable state and federal regulations.

6.3.2 FORMULATION, APPEARANCE, PACKAGING, AND LABELING

The identities and instructions for administration, storage, and handling of cabozantinib and pembrolizumab are described below. Both Cabozantinib and pembrolizumab are considered as, and referred to as, trial drug(s) or trial treatment in this protocol.

Cabozantinib: Chemical Name: *N*-(4-[(6,7-dimethoxyquinolin-4-yl)oxy]phenyl)-*N'*-(4-fluorophenyl)cyclopropane-1,1- dicarboxamide, (2S)-hydroxybutanedioate

Cabozantinib Tablets (XL184): Exelixis will provide investigator with adequate supplies of cabozantinib, which will be supplied as freebase 60-mg, and 20-mg yellow film-coated tablets. The 60-mg tablets are oval, and the 20-mg tablets are round. See Exelixis Study Pharmacy Manual.

Schedule, route of administration and dose: Subjects will receive cabozantinib orally. The cabozantinib dosing will vary according to the dosing levels in phase 1b and the final decided dose for phase 2 part of the trial. In all subjects, dose reductions and delays to manage toxicity are allowed under the guidelines.

Pembrolizumab [Keytruda® (US)], (commercially available) a humanized monoclonal antibody against the PD-1 protein, has been developed by Merck & Co for the treatment of cancer. Pembrolizumab may be supplied in 2 different formulations:

Pembrolizumab injection is supplied as a sterile, preservative-free, clear to slightly opalescent, colorless to slightly yellow solution that requires dilution for intravenous infusion. Each vial contains 100 mg of pembrolizumab in 4 mL of solution. Each 1 mL of solution contains 25 mg of pembrolizumab and is formulated in: L-histidine (1.55 mg), polysorbate 80 (0.2 mg), sucrose (70 mg), and water for injection, USP.

OR

- Pembrolizumab powder for solution for injection is a sterile, non-pyrogenic lyophilized powder for intravenous infusion supplied in single-use glass vial

containing 50 mg of pembrolizumab. The product is preservative-free, white to off-white powder, and free from visible foreign matter.

6.3.3 PRODUCT STORAGE AND STABILITY

All study medications will be stored as described in the pharmacy manual and inventoried in accordance with applicable state and federal regulations. Cabozantinib must be stored at room temperature. The tablets are meant to be taken PO only and not be crushed from dissolving in liquid or administered through other routes including PEG tube.

6.3.4 PREPARATION

Cabozantinib capsules and tablets are meant to be taken orally only and not to be opened or crushed for dissolving in liquid or administered through other routes including percutaneous endoscopic gastrostomy (PEG) tubes. Cabozantinib capsules and tablets should not be administered to subjects who do not have adequate swallowing capacity. Cabozantinib is meant to be taken without food (subjects should not eat for at least 2 h before and at least 1 h after taking cabozantinib) with a full glass (at least 8 ounces or 240 mL) of water. If a dose is missed, the missed dose should not be taken less than 12 h before the next dose.

6.4 MEASURES TO MINIMIZE BIAS: RANDOMIZATION AND BLINDING

The study is non-randomized and open label.

